#### **24.3.6** Simulating *T*29

Once a participant's values  $A, B, X_4^*, S_{S29,1}^*$  are generated, then we initially simulate the participant's  $T_{29}$  value from an exponential distribution with rate parameter defined by the input parameters and the Cox model (26) or (27). If  $T_{29} < T_{57} + 28$ , then the value of  $T_{29}$  is kept. If  $T_{29} \ge T_{57} + 28$ , then we set the final value of  $T_{29} = T_{57} + 28$  plus a draw from a random uniform distribution over -3 to 3 days rounded to the nearest day (to account for visit window variability).

## 24.3.7 Simulating $C_{29}$ and $\Delta_{29}$

For simplicity, we do not allow dropout between the Day 29 visit and the Day 57 visit. Therefore, we set  $C_{29} = C_{57} + 28$ . Then we set  $\Delta_{29} = I(T_{29} \leq C_{29})$ . Note that, because in the analysis outcomes for Day 29 correlates analyses are only counted starting 7 days post Day 29 visit, cases with  $T_{29} < 7$  are excluded from the analysis (this is handled in the data analysis code, not in the data set construction code).

## **24.4** Simulating the subcohort indicator R

The subcohort indicator R is one if a participant is sampled for measurement of  $(S_1, S_{29}, S_{57})$ .

#### **24.4.1** Input parameters for simulating R

We simulate R following Table 5 in this SAP, where the six baseline demographic strata are:

- 1.  $X_4 \ge 65$  and  $X_3 = 0$  (minority)
- 2.  $X_4 \ge 65$  and  $X_3 = 1$  (non-minority)
- 3.  $X_4 < 65$  and  $X_1 = 1$  (at-risk) and  $X_3 = 0$
- 4.  $X_4 < 65$  and  $X_1 = 1$  (at-risk) and  $X_3 = 1$
- 5.  $X_4 < 65$  and  $X_1 = 0$  (not at-risk) and  $X_3 = 0$

6.  $X_4 < 65$  and  $X_1 = 0$  (not at-risk) and  $X_3 = 1$ 

For each of the 24 subgroups/cells defined by (a, b) cross-classified with the above 6 demographic subgroups (as in Table 5), define the total numbers to be sampled into the immunogenicity subcohort, n2(a, b, c) for  $a = 0, 1, b = 0, 1, c = 0, \dots, 6$ . Then, for each subgroup (a, b, c), R is set to 1 for a random sample of size n2(a, b, c) without replacement. Lastly, all non-cases (with  $\Delta = 0$ ) and R = 0 have all three values  $(S_1, S_{29}, S_{57})$  set to NA.

The default settings for n2(a, b, c) to match Table 5 in the SAP are as follows:

- n2(1,0,c) = 150 for  $c = 1, \dots, 6$
- n2(0, 0, c) = 20 for  $c = 1, \dots, 6$
- n2(1, 1, c) = 50 for  $c = 1, \dots, 6$
- n2(0, 1, c) = 50 for  $c = 1, \dots, 6$

### 24.4.2 Per-protocol indicator

Lastly, we simulate the per-protocol (PP) indicator variable, which is 1 if both immunizations at Day 0, 29 were received and there were no specified protocol violations.

Input parameter:

 $P_{PP=1}$  = Probability a participant is per-protocol (default = 0.99)

 $P_{PP=1}$  is simulated from a Bernoulli random variable with success probability  $P_{PP=1}$ . The Day 57 marker correlates analyses are done in individuals with  $P_{PP=1}$ .

## 24.4.3 Variables output for the data set

The following collates all of the variables defined for the simulated data set.

- A
- B
- $X_1, \cdots, X_5$

- PP
- R
- $S_{1.1}, \cdots, S_{1.5}$
- $S_{29.1}, \cdots, S_{29.5}$
- $S_{57.1}, \cdots, S_{57.5}$
- $\tilde{T}_{29}, \Delta_{29}$
- $\tilde{T}_{57}, \Delta_{57}$

## 25 Appendix: Notes on Planning for Stage 2 Correlates Analyses

The paper Sun, Zhou, Gilbert (submitted) "Analysis of Cox model with Longitudinal Covariates with Measurement Errors and Partly Interval-Censored Failure Time, with Application to an AIDS Clinical Trial" may be a suitable method for assessing antibody markers over time as correlates of the SARS-CoV-2 infection endpoint, once there is follow-up data for more than a year with antibody markers measured at all time points up to at least a year. The paper extends Fu and Gilbert (2017) from right-censored failure time data to partly interval-censored failure time data, which means a composite endpoint is analyzed with one component subject to right-censoring and the other component subject to interval censoring. In our application, the COVID primary endpoint is subject to right-censoring, and seroconversion is subject to interval-censoring.

# 26 Appendix on Stochastic VE Analysis Project

We consider an approach that simply implements the stochastic VE analysis as specified in the SAP, using a grid of mean shifts, and then the results are interpreted by marking the mean shifts corresponding to expected shifts under each of the SARS-CoV-2 variants considered in the [name] panel used in the phase 1 study. With this mindset, this is a data analysis project, not a new methods project. Let  $S_0$  denote D57 antibody level to the D614G strain, and  $S_v$  denote D57 antibody level to variant v. Let  $p_{cc}$  be the density of baseline covariates L in the case-cohort study. We make the following assumption:

**A.1** 
$$E_{cc}[S_0|L] = E_{Ph1}[S_0|L].$$

Let  $\hat{E}_{cc}[S_0|L]$  be an estimator of  $E_{cc}[S_0|L]$  from the case-cohort data.

Suppose there are *n* participants in the phase 1 study with data on  $S_0$  and *L*. Let  $\mu_0^{std.cc}$  be the mean of  $S_0$  in the phase 1 sample standardized/transported to the distribution of *L* in the case-cohort study. We estimate  $\mu_0^{std.cc}$  by

$$\hat{\mu}_0^{std.cc} = \sum_{i=1}^n \hat{E}_{cc}[S_0|L_i]\hat{p}_{cc}(L_i),$$

where assumption A.1 is needed for this estimate to be unbiased.

Next, we need a way to estimate  $\mu_v^{std.cc}$ . This is challenging given that  $S_v$  is only measured in between 10 and 28 vaccine recipients in the phase 1 trial. Because of the small sample size, we make the assumption that

$$E_{cc}[S_v|L] - E_{cc}[S_0|L] = E_{ph1}[S_v] - E_{ph1}[S_0],$$

and then we estimate  $E_{cc}[S_v|L]$  by

$$\hat{E}_{cc}[S_v|L] = \hat{E}_{cc}[S_0|L] + \left(\bar{S}_v - \bar{S}_0\right),\,$$

where  $\bar{S}_0$  is the sample average of the  $S_0$  measurements in the phase one trial and similarly for  $S_v$ .

In conclusion, for a given variant v, the mean shift of focus for interpreting the result of the stochastic VE analysis is

$$\Delta_v = \hat{E}_{cc}[S_0|L] - \hat{E}_{cc}[S_v|L]$$

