In particular, conditional density estimates of immune response markers will be principally based on a nonparametric estimation strategy that reconstructs the conditional density through estimates of the conditional hazard of the discretized immune response marker values (Hejazi et al., 2020a,d,c); this approach is an extension of the proposal of Díaz and van der Laan (2011). A Super Learner ensemble (van der Laan et al., 2007) of variants of this nonparametric conditional density estimator and semiparametric conditional density estimators based on Gaussinization of residuals will be constructed using the s13 R package (Coyle et al., 2020). In settings with limited numbers of case endpoints, the outcome process will be modeled as a Super Learner ensemble of a library of parametric regression techniques (as recommend by Gruber and van der Laan, 2010), while the library will be augmented with flexible regression techniques — including, for example, lasso and ridge regression (Tibshirani, 1996; Tikhonov and Arsenin, 1977; Hoerl and Kennard, 1970), elastic net regression (Zou and Hastie, 2003; Friedman et al., 2009), random forests (Breiman, 2001; Wright et al., 2017), extreme gradient boosting machines (Chen and Guestrin, 2016), light and efficient gradient boosting machines (Ke et al., 2017), multivariate adaptive polynomial and regression splines (Friedman et al., 1991; Stone et al., 1994; Kooperberg et al., 1997), and the highly adaptive lasso (van der Laan, 2017; Benkeser and van der Laan, 2016; Hejazi et al., 2020b) — as the number of endpoint cases grows.

These algorithm libraries will be coordinated to match those used in other CoP analyses.

Additionally, we recall that P(Y(0) = 1) = P(Y = 1 | A = 0) (in view of vaccine versus placebo randomization, as stated previously in Section 15.1) and may be estimated in the same way as for the analysis of controlled vaccine efficacy, thus yielding an estimate of stochastic interventional VE defined by

$$SVE(\delta) = 1 - \frac{E[P(Y=1 \mid A=1, S=S+\delta, X=x) \mid A=1, X]}{P(Y(0)=1)}.$$

Output of the analyses will be presented as point and 95% point-wise confidence interval estimates of  $E[Y(1, S(1)+\delta)]$  and of SVE(s) over the values of s for each of the Day 57 antibody markers, for each of a range of  $\delta$  spanning -2 to 2 on the standard unit scale for each antibody marker.

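### Section 26 does not restrict the variant antibody shift to paired sera, and marks it on the SVE curve with no error of its own

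*Combined protocol and SAP*

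**What the plan says.** Section 26 (Appendix on Stochastic VE Analysis Project) writes S0 for the Day 57 antibody level to D614G and Sv for the level to variant v. It runs the Section 15.2 analysis over a grid of mean shifts, after which "the results are interpreted by marking the mean shifts corresponding to expected shifts under each of the SARS-CoV-2 variants considered" in a phase 1 panel.

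Under assumption A.1 it posits n "participants in the phase 1 study with data on" S0 and the baseline covariates L; no value of n is given. Sv, by contrast, "is only measured in between 10 and 28 vaccine recipients in the phase 1 trial". Citing those low numbers, the section assumes that the variant-minus-D614G mean difference at every L equals the marginal phase 1 difference. The estimator then adds (Svbar - S0bar) to the fitted D614G mean. S0bar is the sample average of the S0 "measurements in the phase one trial and similarly for" Sv. The shift of interest is the fitted D614G mean minus the fitted variant mean. Section 26.1 says that with no L available in phase 1 the shift is simply S0bar - Svbar.

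Section 15.2 sets the reporting: "Output of the analyses will be presented as point and 95% point-wise confidence interval estimates of" the counterfactual risk and SVE, for shifts "spanning -2 to 2 on the standard unit scale for each antibody marker". Neither section gives a standard error, interval or bootstrap for the variant shift itself.

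**The concern.** Two separate matters arise.

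First, S0bar carries no variant index and is defined over the phase 1 D614G measurements, while Svbar covers only those tested for variant v. The count of 10 to 28 reads most naturally as differing by variant, and a single S0bar cannot match several different tested subsets. For any variant not tested in everyone with S0, the two means then come from different sets of people. Differences in titre between people enter the shift, although anyone with both titres could supply a within-person difference.

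Second, the shift decides where on the curve a variant is read. The pointwise SVE interval holds for a given shift. At a variant's mark the shift is itself an estimate from 10 to 28 people, and that error is left out. The SAP does propagate an estimated input elsewhere: Section 14 refits the learned baseline immunogenicity predictor within every bootstrap sample.

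**Working it through.** There is no plan figure to reproduce, because the documents state no precision for the shift.

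**Step 1. What the shift is.** Substituting the Section 26 estimators:

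shift = E[S0|L] - {E[S0|L] + (Svbar - S0bar)} = S0bar - Svbar.

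L cancels, so the form that Section 26.1 gives for the no-covariate case holds in every case.

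**Step 2. Inputs.**
- m, people with Sv: 10 to 28 (Section 26).
- n, people with S0: not given. Assumed from n = m upwards, with the m nested in the n.
- rho, within-person correlation of S0 and Sv: not given. Assumed 0 to 0.95. The Day 57 simulation defaults for baseline-negative vaccinees in Section 24.2.1 are 0.7 in general, 0.8 for Spike with RBD and 0.9 for ID50 with cID80. All are correlations between different readouts, not between D614G and a variant, so they only indicate a range.
- s, the SD of either titre: assumed equal for both, and equal to the standard unit of the Section 15.2 grid.

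**Step 3. Standard errors.** With nesting, Cov(S0bar, Svbar) = rho s²/n, so
- as written: Var = s² (1/m + 1/n - 2 rho/n);
- paired, same m people: Var = 2 s² (1 - rho)/m;
- SE ratio (as written / paired) = sqrt{[1 + (m/n)(1 - 2 rho)] / [2(1 - rho)]}.

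Example with m = 10, n = 28, rho = 0.9. As written: sqrt(0.1000 + 0.0357 - 0.0643) = 0.267 s. Paired: sqrt(0.2/10) = 0.141 s. Ratio 1.89.

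| m | n | rho 0 | 0.5 | 0.7 | 0.8 | 0.9 | 0.95 |
|---|---|---|---|---|---|---|---|
| any | n = m | 1.00 | 1.00 | 1.00 | 1.00 | 1.00 | 1.00 |
| 10 | 28 | 0.82 | 1.00 | 1.20 | 1.40 | 1.89 | 2.60 |
| 10 | 60 | 0.76 | 1.00 | 1.25 | 1.50 | 2.08 | 2.92 |
| 28 | 60 | 0.86 | 1.00 | 1.16 | 1.34 | 1.77 | 2.41 |
| any | very large | 0.71 | 1.00 | 1.29 | 1.58 | 2.24 | 3.16 |

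A simulation at m = 10, n = 60, rho = 0.9 gave 2.09 against 2.08 from the formula. With the variant SD at 0.8 or 1.2 times the D614G SD, the ratio for m = 10, n = 60 is 1.09 or 1.32 at rho 0.7, and 1.68 or 2.11 at rho 0.9.

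**Step 4. Error of the shift even when paired.** The 95% half-width is 1.96 × sqrt(2(1 - rho)/m), in SD units:

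| m | rho 0.5 | 0.7 | 0.9 |
|---|---|---|---|
| 10 | 0.62 | 0.48 | 0.28 |
| 28 | 0.37 | 0.29 | 0.17 |

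So the mark is uncertain by roughly 0.2 to 0.6 SD either way on a grid running from -2 to 2.

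**The case against.** The strongest objection is that unpaired averaging is not established. Section 26 never gives n, never relates n to the 10 to 28, and does not say that every D614G serum enters S0bar. If S0bar is taken over the same sera as Svbar, the difference of means is exactly the mean within-person difference and nothing is lost. This stands, and it makes the first point conditional. The literal text still leans the other way, since S0bar has no variant index.

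Second, the pointwise interval in Section 15.2 is correct for its own estimand, SVE at a stated shift, and the variant marks are an aid to interpretation. This also stands. The omission matters once SVE is read or quoted at a variant's mark, which is what the marks are for.

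Some stronger inferences are tempting but unsupported:
- A reader might conclude that the error is up to about twice what the data allow. Two is neither a typical value nor a bound. At rho 0.9 it needs n = 4m (40 for m = 10, 112 for m = 28); at rho 0.95 the ratio can exceed 3; below rho 0.5 the written formula is the more precise one. Nor does marking the shift as a point inflate its standard error, so the two faults should not be run together.
- One might infer bias from non-random choice of sera. The documents do not say how the sera were chosen.
- One might quote a coverage failure at the mark. A calculation with m = 10, n = 28, SD 0.8 log10 and rho 0.9 gives 78% to 92% for a nominal 95% interval. It also assumes 50 vaccine and 250 placebo cases, a true shift of 0.8 log10, hazard ratios of 0.3 to 0.6 per 10-fold and a log-linear risk model. At m = 28 the figure is about 93% to 95%, and the nonparametric estimator of Section 15.2 was not evaluated.
- One might infer that variants are ranked on these shifts. No such ranking is planned.

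**Conclusion.** The point holds in a limited form. Followed literally, Section 26 compares a D614G mean with a variant mean without requiring the same people, and it attaches no uncertainty to the result. The cost of not pairing runs from none (same sera) to a standard error 1.2 to 2.6 times the paired one at correlations 0.7 to 0.95 for an assumed 10 of 28 sera; below a correlation of 0.5, pairing would cost precision. These figures depend on n, rho, nesting and equal SDs, none of which the documents supply.

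The missing uncertainty does not depend on how S0bar is read: a paired shift still has a 95% half-width of about 0.2 to 0.6 SD for correlations 0.9 to 0.5.

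Severity is low. Section 26 is an interpretive appendix in tentative terms, and the planned correlates of risk and protection estimates, tests and multiplicity families do not change.

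**What to change.** In Section 26, for each variant separately, replace S0bar - Svbar by the mean of S0i - Svi over phase 1 participants with both titres measured at Day 57 in the same assay. State the number of pairs. This keeps the SAP's sign and equals the current estimate when the sera coincide.

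Show the 95% interval of each shift on the SVE plot. Use a t-based interval or a small-sample-corrected bootstrap. A plain percentile bootstrap of 10 differences would itself cover only about 90%: its half-width is roughly 1.96 × sqrt(9/10) = 1.86 standard errors, close to the two-sided 90% t quantile on 9 degrees of freedom (1.83).

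For any SVE quoted at a variant's mark, give an interval that also propagates the error of the shift, for example by drawing the shift together with the SVE fit.

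The cost is a sentence or two of SAP text and a few lines of code, with no new data. The downsides are that D614G values from people not tested for the variant go unused, which loses precision only if the within-person correlation is below about 0.5, and that the interval shown for a variant becomes wider.

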## 15.2 CoP: Stochastic Interventional Effects on Risk and Vaccine Efficacy

Another approach to studying correlates of protection involves estimating the effect of shifting the immune response marker distribution in the vaccinated individuals (Hejazi et al., 2020a). Specifically, we can consider the effect on

risk of a given endpoint of a controlled intervention that shifts the distribution of an immune response by  $\delta$  units, where  $\delta$  is an analyst-specified real number. Considering a counterfactual scenario in which we are able to intervene so as to modify the immune response induced by the vaccine (e.g., a hypothetical change in dose or other re-formulation of the vaccine), we take this hypothetical intervention to lead to an improved (if  $\delta > 0$ ) or lessened immune response (if  $\delta < 0$ ) relative to the current vaccine (at  $\delta = 0$ ). Using this framework, we can query the counterfactual risk of the endpoint under this hypothetical vaccine. Using notation established above, this quantity can be expressed as the mean of the counterfactual variable  $Y(1, S(1) + \delta)$ .

This approach is similar to the controlled effects approach described in Section 15.3, but with an important distinction. In the controlled effects approach, one assumes that it is possible to set S = s for all individuals in the population. For high values of s, this assumption may be unrealistic if the vaccine fails to be strongly immunogenic for some subpopulations. On the other hand, with the interventional approach, it is only required that individuals' immune responses be shifted relative to their observed immune response, which may be more plausible for some vaccines.

Under assumptions (Hejazi et al., 2020a), the main two of which being no unmeasured confounding and positivity (forms of both are also required for the Controlled VE CoP analyses), the counterfactual risk of interest  $E[Y(1, S(1) + \delta)]$  is identified by

$$E[P(Y = 1 \mid A = 1, S = S + \delta, X = x) \mid A = 1, X].$$

Examining this quantity across a range of  $\delta$  provides insight into the relative contribution of a given immune response marker in preventing the endpoint of interest.

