#### 26.1 Remarks

The estimator of  $\hat{\mu}_0^{std.cc}$  requires that we have data on the same baseline covariates L that are used in the case-cohort study for estimation of  $E_{cc}[S_0|L]$ .

If we do not, then we may need to simplify the estimator of  $E_{cc}[S_0|L]$  to only include a few covariates L collected in both studies. In the most extreme case, with no L available in the phase one study, we simply take as the estimate of  $\hat{\mu}_0^{std.cc}$  the sample average of  $S_0$  values in the phase 1 study,  $\bar{S}_0$ . In this case  $\Delta_v$  is simply taken to be  $\bar{S}_0 - \bar{S}_v$ .

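### The variant mean shift in the stochastic-VE appendix has the opposite sign to the delta axis on which it is to be marked

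*Combined protocol and SAP*

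**What the plan says.** Section 15.2 studies the counterfactual outcome `Y(1, S(1) + δ)`. On the direction of δ it says "we take this hypothetical intervention to lead to an improved" response when δ is positive; negative δ means a lessened response, and δ = 0 is the current vaccine. Results are reported over a range of δ "spanning -2 to 2 on the standard unit scale for each antibody marker".

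Section 26 keeps that analysis as specified and adds an interpretive step: "the results are interpreted by marking the mean shifts corresponding to expected shifts under each of the SARS-CoV-2 variants considered". The reference marker `S_0` is said to "denote D57 antibody level to the D614G strain", and `S_v` is the corresponding level to variant v. The section then estimates the variant mean as `Ê_cc[S_v|L] = Ê_cc[S_0|L] + (S̄_v − S̄_0)`. It concludes that "the mean shift of focus for interpreting the result of the stochastic VE analysis is" `Δ_v = Ê_cc[S_0|L] − Ê_cc[S_v|L]`.

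Section 26.1 covers missing covariates: "In the most extreme case, with no L available in the phase one study", `Δ_v` "is simply taken to be" `S̄_0 − S̄_v`.

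**The concern.** The appendix exists to show where each variant sits on the SVE(δ) curve. That placement is meaningful only if the variant's shift and the curve's δ axis share a sign convention, and they do not. The axis counts a loss of response as negative; the appendix counts a loss relative to D614G as positive.

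The grid is symmetric about zero, so a value with the wrong sign still falls inside it and nothing flags the mistake. On a rising curve, the reader would conclude that a variant which escapes neutralisation is better protected against than the vaccine-matched strain. The SAP is also offered to other groups to implement, so the formula may be coded by people who did not write it.

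**Working it through.** **Inputs from the SAP**
- Direction of δ: `S(1) + δ`, negative for a lessened response (section 15.2).
- Variant mean and `Δ_v`: sections 26 and 26.1.
- Expected direction of efficacy with the marker: non-decreasing. This is stated for controlled VE in section 15.1.
- VE of 0.90 at δ = 0: the default in the simulation appendix, section 24.3.1. Used for illustration only.

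**Inputs assumed** (the SAP gives none for the variants)
- Drop in mean log10 titre: 0.4 or 0.8, with 0.3 to 0.8 as a wider range.
- Risk ratio (RR) per 10-fold titre: 0.3, 0.4 or 0.6, with 0.25 to 0.6 as a wider range.

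**Step 1: reproduce the plan's formula.** Substitute the appendix's own estimate of the variant mean:

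`Δ_v = Ê_cc[S_0|L] − {Ê_cc[S_0|L] + (S̄_v − S̄_0)} = S̄_0 − S̄_v`

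The term in L cancels, so this holds for every L and agrees with section 26.1. The two sections are consistent with each other.

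**Step 2: compare with the axis.** The appendix's expression for the variant mean already has the form `S_0 + δ`, with `δ = S̄_v − S̄_0`. The defined `Δ_v` is exactly minus that. If `S̄_v < S̄_0`, the shift on the axis is negative but `Δ_v` is positive.

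**Step 3: size of the misreading.** With rare events and risk log-linear in the marker, `SVE(δ) = 1 − (1 − 0.90) × RR^δ`, δ in log10 units. For example, at RR 0.3 and a 0.8 drop:
- correct sign: `1 − 0.10 × 0.3^(−0.8) = 0.738`
- as written: `1 − 0.10 × 0.3^(0.8) = 0.962`

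| Drop (log10) | RR per 10-fold | SVE at −drop (correct sign) | SVE at +drop (as written) |
|---|---|---|---|
| 0.8 | 0.3 | 0.738 | 0.962 |
| 0.8 | 0.4 | 0.792 | 0.952 |
| 0.8 | 0.6 | 0.850 | 0.934 |
| 0.4 | 0.3 | 0.838 | 0.938 |
| 0.4 | 0.4 | 0.856 | 0.931 |
| 0.4 | 0.6 | 0.877 | 0.918 |

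Over the wider ranges, the as-written reading runs from 0.914 to 0.967, always above 0.900. The correctly signed reading runs from 0.697 to 0.883, always below it.

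A Monte Carlo g-computation with RR 0.4, drop 0.5, marker SD 0.8 and placebo risk 0.10 gives 0.900 at δ = 0, 0.937 as written and 0.843 with the sign corrected. The closed form gives 0.937 and 0.842.

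**Step 4: flat curve.** With RR = 1, SVE is 0.90 at every δ and the sign has no effect.

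**The case against.** **`Δ_v` may be meant as the size of a decrement.** The SAP never writes `δ = Δ_v`. An analyst who knows that negative δ means a weaker response could mark the variant on the correct side unprompted. That is possible, and defining the marked point as `δ = −Δ_v` would resolve the matter equally well. But the text calls `Δ_v` a mean shift, has shifts marked on a signed axis and states no reversal. Followed literally, it puts the variant on the wrong side.

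**The efficacy figures rest on assumed inputs.** This stands. The simulation default for the marker effect is null (section 24.3.1), and the misreading of VE needs a rising curve. The sign mismatch itself needs no assumption.

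**A reader might infer that the scale is wrong too**, because neutralisation markers are log10 titres in section 2.1 while the grid is in standard units. The documents do not establish this. The term is not defined, and section 26 speaks only of antibody level, so its quantities may already be on the grid's scale. If the grid is in SD units and raw log10 shifts were marked on it, the effect would probably be smaller than that of the sign. The simulation defaults suggest Day 57 SDs of roughly 0.7 to 0.98, though that list is hard to read in the available text. For a 0.5 log10 drop at RR 0.4, an unconverted shift with the correct sign would read 0.862 (SD 0.7) or 0.843 (SD 0.98) instead of 0.842.

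**The appendix is exploratory.** This also stands. Estimation of SVE(δ), the analyses in Table 10, and the multiplicity procedures in sections 12.4.2 and 16.2 do not use `Δ_v`.

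**Conclusion.** The sign in sections 26 and 26.1 is opposite to the convention of section 15.2. This follows from the SAP's definitions alone. Marked as written, any variant with a lower mean response than D614G falls on the improved-response side. Its VE is then read as higher than for the reference strain wherever SVE(δ) rises with the marker. On the assumed inputs, with VE 90% at δ = 0, a 0.8 log10 drop reads as 93–96% instead of 74–85%, and a 0.4 log10 drop as 92–94% instead of 84–88%. With a flat curve there is no effect.

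Two stronger conclusions are not supported. One is that a scale error has been shown; only an unstated unit has. The other is that the trial's correlate findings are compromised; no CoR or CoP test uses this quantity. The point is a should-fix.

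**What to change.** In section 26, define `Δ_v = Ê_cc[S_v|L] − Ê_cc[S_0|L]`, which equals `S̄_v − S̄_0`. In section 26.1, change the no-covariate case to `S̄_v − S̄_0`. Add a sentence saying that a negative value means a weaker response to the variant and is marked at that δ on the SVE(δ) curve.

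As a clarification, state the unit of `Δ_v` and define the standard unit scale in section 15.2. If it means SD units, divide `Δ_v` by the SD used for the δ grid before marking it.

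The cost is two formula edits and a sentence or two of text. No new data or re-estimation of the SVE curve is needed.
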